## 7.5 Supportive Care

All treatments that the investigator considers necessary for a subject's welfare may be administered at the discretion of the investigator in keeping with the community standards of medical care. All concomitant medication will be recorded on the eCRF, including all prescription, over-the-counter, herbal supplements, and IV medications and fluids. If changes occur during the study period, documentation of drug dosage, frequency, route, and date may also be included on the eCRF.

The subject needs to notify the investigational site about any new medications he/she takes after the start of the study drug. All medications (other than study drug) and significant nondrug therapies (including physical therapy and blood transfusions) administered after the subject starts treatment with study drug must be listed on the Concomitant Medications/Significant Nondrug Therapies After Start of Study Drug eCRF.

The use of prophylactic growth factors are not permitted during Part 1. However, during Part 2, neutrophil growth factors may be used at the treating investigator's discretion based on American Society of Clinical Oncology guidelines for the use of WBC growth factors (Smith et al., 2006). The use of erythropoietin will be in strict compliance with FDA recommendations in the current prescribing information. Bisphosphonates are allowed while subjects are receiving study

treatment. The use of intravenous immunoglobulin is allowed while subjects are receiving study treatment as per institutional guidelines.

**Flu-like symptoms** (fever, headache, myalgias, arthralgias) may be treated with aspirin, Tylenol, NSAIDs, or antihistamines as clinically indicated per the investigators' judgment.

**Diarrhea** may be treated initially with loperamide as clinically indicated, with additional interventions per the investigators' judgment.

**Nausea and vomiting** may be treated with 5HT3 receptor antagonists as clinically indicated, with additional interventions per the investigators' judgment.

**Hematologic support** with granulocyte-colony stimulating factor and/or transfusions of packed red blood cells and/or platelets may be given as clinically indicated after completion of the DLT period, per ASCO, NCCN or institutional guidelines. It is prohibited during the first 28 days of the study. The use of erythropoietin, romiplostin, and eltrombopag will be in strict compliance with FDA recommendations in the current prescribing information.

Itacitinib has the potential to cause WBC margination (i.e., a transient decrease in absolute neutrophil count [ANC]), assessment of hematology parameters should be performed before study drug administration at all applicable study visits.

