### 5.1 Inclusion Criteria

**Yes/No (Response of "no" = patient ineligible)**

- 5.1.1 \_\_\_\_\_ Male or female subject aged  $\geq 18$  years.
- 5.1.2 \_\_\_\_\_ Active, clinically diagnosed, moderate or severe chronic GVHD as defined by the NIH Consensus Development Project Criteria (See Appendix 2).
- 5.1.3 \_\_\_\_\_ History of an allogeneic hematopoietic cell transplant with any conditioning regimen, donor, or graft source.
- 5.1.4 \_\_\_\_\_ Need for systemic treatment for chronic GVHD as assessed by the treating investigator.
- 5.1.5 \_\_\_\_\_ No previous systemic treatment for chronic GVHD.
- Note: Participants may be receiving immunosuppressants for the prophylaxis or treatment of acute GVHD, but these medications must have been stable for at least 2 weeks prior to the initiation of study therapy. Prednisone dose (or its equivalent) should be at doses of  $\leq 0.25$  mg/kg/d for at least 2 weeks prior to the initiation of study therapy.
- Topical or inhaled treatments for chronic GVHD are allowed. Any prior ECP treatments for the management of acute GVHD must have occurred  $> 4$  weeks prior to the initiation of itacitinib treatment.
- 5.1.6 \_\_\_\_\_ Able to swallow and retain oral medication.
- 5.1.7 \_\_\_\_\_ Life expectancy  $> 24$  weeks.
- 5.1.8 \_\_\_\_\_ Karnofsky performance status  $\geq 60$
- 5.1.9 \_\_\_\_\_ Evidence of myeloid and platelet engraftment:
- Absolute neutrophil count  $\geq 1000/\text{mcL}$
  - Platelet count  $\geq 25,000/\text{mcL}$

Note: Use of growth factors and transfusion support is allowed during the study; however, growth factors and transfusion support to reach a minimum ANC or

platelet count for inclusion are not allowed within the 7 days before the screening laboratory assessment.

**5.1.10** \_\_\_\_\_ Adequate organ function as defined as:

- **Hepatic:**
  - Total bilirubin  $\leq 2$  mg/dL
  - AST(SGOT)/ALT(SGPT)  $\leq 2.5 \times$  institutional ULN (unless of non-hepatic origin). AST/ALT  $\leq 5 \times$  ULN is acceptable if associated with chronic GVHD.
- **Renal:**
  - eGFR  $\geq 30$  mL/min/1.73 m^2 as calculated using the Modification of Diet in Renal Disease formula or by the Cockcroft-Gault formula:
    - Males:  $\frac{(140 - \text{age}) \times \text{weight}[\text{kg}]}{\text{serum creatinine} \left[ \frac{\text{mg}}{\text{dL}} \right] \times 72}$

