### **6.5 Ancillary Therapy and Supportive Care**

Topical corticosteroid therapy and regimens to treat or prevent bronchiolitis obliterans (e.g., inhaled corticosteroids) may be continued per institutional guidelines.

Other supportive medications in accordance with standard clinical practice (such as for emesis, diarrhea, osteoporosis etc.) are permitted. Use of neutrophil growth factors (filgrastim and pegfilgrastim), red blood cell growth factors (erythropoietin) or TPO receptor agonists (romiplostim, eltrombopag) is permitted per institutional policy for Part 2 participants only. Transfusions may be given in accordance with institutional policy.

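### Section 7.5 bars red cell and platelet transfusion until the DLT period ends, while Section 6.5 allows it and Table 3 foresees it in that window

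*Combined protocol and SAP*

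**What the plan says.** The paragraph on hematologic support in Section 7.5 covers G-CSF and blood products together. It says that "transfusions of packed red blood cells and/or platelets may be given as clinically indicated after completion of the DLT period", and then: "It is prohibited during the first 28 days of the study". Neither sentence refers to Part 1 or makes an exception for ECP. The same section opens with a general clause that whatever the investigator considers necessary for a patient's "welfare may be administered at the discretion of the investigator in keeping with the community standards of medical care".

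Section 6.5 says: "Transfusions may be given in accordance with institutional policy". The sentence before it covers neutrophil and red cell growth factors and TPO receptor agonists, whose use "is permitted per institutional policy for Part 2 participants only". That limit does not extend to transfusion.

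Table 3 in Section 4.3 defines DLTs. It says that platelets given so that ECP can go ahead are not a DLT. Its criterion for grade 3 or higher bleeding names transfusion among the signs of severity. Exclusion 5.2.15 removes patients unwilling to receive blood components. Section 6.6.4 restricts TPO receptor agonists and erythropoietin within the DLT period but does not list transfusion.

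On growth factors, 7.5 says: "The use of prophylactic growth factors are not permitted during Part 1", followed by "However, during Part 2, neutrophil growth factors may be used".

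**The concern.** Transfusion is a safety measure, and the plan gives sites opposite instructions on it in the window when the dose is being judged. Taken at its word, 7.5 withholds blood products during the first cycle of twice-weekly ECP from patients who may enter with platelets of 25,000/mcL (5.1.9). A site following 6.5 would transfuse under local policy. With up to four centers taking part (4.6), practice could differ between them while platelet, bleeding and anemia criteria are being scored.

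G-CSF has a related conflict. The early ban in 7.5 is not limited to Part 1, although 6.5 and 7.5 itself allow neutrophil growth factors in Part 2. For Part 1 after the DLT period, 7.5 allows G-CSF and 6.5 does not.

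**Working it through.** There is no sample size, power or error rate to reproduce. The check compares the texts and then sets out which days and patients are covered.

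**1. Is transfusion allowed in the DLT window?**

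| Place | Answer | Limit stated |
|---|---|---|
| 7.5, hematologic support | No | Until the DLT period ends; also the first 28 days |
| 6.5 | Yes | Institutional policy only |
| 4.3, Table 3 | Presupposed, for ECP platelets and for bleeding | None |
| 5.2.15 | Presupposed (patients must accept it) | None |
| 6.6.4 | Not listed as prohibited | None |

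Section 4.3 applies Table 3 only to events in the DLT period, so its platelet bullet concerns exactly the days that 7.5 closes. Of these five places, only 7.5 says no.

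**2. Which days?** The DLT period runs from the first lead-in dose to cycle 1 day 28 (4.3). The lead-in is 5 to 10 days (Table 7, footnote 2), nominally 7 (4.1).

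- DLT period = lead-in + 28 = 33 to 38 days; nominally 7 + 28 = 35.
- If the 28 days of the study are counted from the first itacitinib dose (an assumption, since 7.5 gives no start), that ban ends 5 to 10 days before the DLT period does.

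So the two sentences in 7.5 may not even agree with each other on when the restriction lifts.

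**3. Which patients?** Part 1 has 6 to 18 patients (4.2, 4.5). The conflict exists there on any reading, because the DLT window is a dose-finding device. Read literally, 7.5 also covers Part 2, which is planned to enroll 40 (4.5).

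**4. How often would blood be needed?** The documents give no figure. Section 2.3 expects a mild fall of 5,000 to 10,000/mcL after an ECP session. From the entry floor, one such fall leaves 25,000 - 10,000 = 15,000 to 25,000 - 5,000 = 20,000/mcL, ignoring recovery and any drug effect. ECP is run under local guidelines (6.1.1, 6.3), and no platelet threshold for the procedure is stated. The number of patients who would need platelets cannot be derived.

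**The case against.** The strongest reply is that no one would be denied blood. The welfare clause opens 7.5. Section 6.6.4 lets normally prohibited therapies be given to protect a participant. Section 16.9 foresees deviations that remove an immediate hazard. Section 7.5 itself lists blood transfusions among the therapies to be recorded once study drug has started.

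Much of this stands as mitigation, but none of it cancels the ban. The welfare clause is general, and the prohibition is specific and comes later in the same section. The 6.6.4 allowance sits in the bullet on investigational medication and takes COVID-19 products as its example. Section 16.9 makes such an act a deviation to be reported promptly, which is different from permitting it.

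A second reply is that Table 3 works as an exception for ECP platelets. It is a rule on what counts as a DLT, 7.5 does not refer to it, and it would not reach red cells.

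A third is that the ban was meant for Part 1 only. That is plausible: 4.3 ties the DLT period to dose finding, and 6.5 and 7.5 separate the parts for growth factors. The transfusion conflict remains in Part 1.

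The 5.1.9 note, "Use of growth factors and transfusion support is allowed during the study", adds little. It is an eligibility note whose working content is the 7-day bar before the screening laboratory test.

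A reader might infer that 46 to 58 patients (6 + 40 to 18 + 40) are affected, or count the ECP sessions that fall under the ban. Such figures measure exposure to a sentence, not need for blood. The patient range also requires the both-parts reading and full Part 2 enrollment.

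**Conclusion.** The concern holds as an internal contradiction on a safety rule. Section 7.5 is the outlier against 6.5, Table 3, 5.2.15 and 6.6.4, and nothing in the documents reconciles them. It certainly applies to the 6 to 18 Part 1 patients. Extension to Part 2 rests on reading 7.5 literally.

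A reader might go further and infer that patients will be refused blood or that dose selection is compromised. The documents do not support either. The mitigating clauses make refusal unlikely to be what was intended, no transfusion rate is given, and no change to the RP2D, type I error or power is shown. The point deserves correction because, followed as written, the rule withholds blood products from patients who may enter with low platelets, and correcting it costs almost nothing.

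**What to change.** In 7.5:

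- Delete the 28-day sentence as it applies to transfusion, together with the condition that transfusion waits for the end of the DLT period.
- State that clinically indicated red cell and platelet transfusions, including platelets required for ECP, are allowed at any time in both parts.
- Limit the G-CSF restriction to Part 1, and align 7.5 with the Part 2-only rule in 6.5 so that the two sections agree. This withdraws the permission that 7.5 now gives Part 1 patients after the DLT period.

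The cost is amendment wording, with no added patients or visits; recording of transfusions is already required by 6.4 and 7.5. One downside is that platelet counts in transfused patients are slightly harder to read against the DLT criterion of a count below 10 x 10^9/L for more than 3 days. Any change to that criterion is optional and separate, and would need a rule for telling transfusion effect from recovery.

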## 8 SCHEDULE OF EVENTS

The Schedule of Events table provides an overview of the protocol visits and procedures. Refer to the Study Procedures section of the protocol for detailed information on each assessment required for compliance with the protocol. The Investigator may schedule visits (unplanned visits) in addition to those listed in the Schedule of Events table in order to conduct evaluations or assessments required to protect the wellbeing of the patient. This Schedule of Events will be followed for the entire study.

**Table 7: Schedule of Events**

Protocol Activities	Screening 	On-Treatment Period: One Cycle = 28 days									Off Treatment Period			
		Lead-In 	Cycle 1		Cycle 2 & 3	Cycle 4	Cycle 5	Cycle 6	Cycle 7	Cycles 8 – 12	PD Visit 	EOT 	Follow-Up 	
Week			1	3	5 & 9	13	17	21	25	29 – 45				
Day of the Cycle (Visit Window)	(-28 days)	-10 to -5 days	1 	15 (+ 3 days)	1 (± 5 days)	1 (± 7 days)	1 (± 7 days)	1 (± 7 days)	1 (± 7 days)	1 (± 7 days)	1 (± 7 days)		30 days from last dose	Every 12 weeks
Informed Consent	X													
Demographics 	X												X	
Medical History	X													
Eligibility Criteria	X													
Registration	X													
Clinical Assessments														
Vital Signs	X	X	X	X	X	X	X	X	X	X	X	X	X	
Physical Exam	X	X	X	X	X	X	X	X	X	X	X	X	X	
Karnofsky Score 	X	X	X	X	X	X	X	X	X	X	X	X	X	
Pulmonary Function Test 	X													
Spirometry 	X					X			X	X 	X	X	X	
2-min walk test 	X		X		X	X		X		X	X	X	X	
ECG	X												X	
Adverse event collection 									X					
Concomitant medications collection									X					
Laboratory Studies														
Hematology 	X	X	X	X	X	X	X	X	X	X	X	X	X	
Chemistry 	X	X	X	X	X	X	X	X	X	X	X	X	X	
Coagulation 	X													
Lipid panel 	X					X			X	X	X	X	X	
Pregnancy Test 	X													

Protocol Activities	Screening 	On-Treatment Period: One Cycle = 28 days									Off Treatment Period			
		Lead-In 	Cycle 1		Cycle 2 & 3	Cycle 4	Cycle 5	Cycle 6	Cycle 7	Cycles 8 – 12	PD Visit 	EOT 	Follow-Up 	
Week			1	3	5 & 9	13	17	21	25	29 – 45			30 days from last dose	Every 12 weeks
Day of the Cycle (Visit Window)	(-28 days)	-10 to -5 days	1 	15 (+ 3 days)	1 (± 5 days)	1 (± 7 days)	1 (± 7 days)	1 (± 7 days)	1 (± 7 days)	1 (± 7 days)	1 (± 7 days)			
HIV and Hepatitis serologies 	X													
Quantitative serum immunoglobulins 	X		X			X			X	X	X	X		
Absolute CD4 Count 	X		X			X			X	X	X	X		
Infection monitoring 	X		X		X	X	X	X	X	X	X	X	X	
Disease Assessments														
Chronic GVHD assessment	X		X 	X	X	X	X	X	X	X	X	X	X	X
Graft failure/ chimerisms 	X					X			X	X	X	X	X	X
Malignancy relapse assessment 	X		X	X	X	X	X	X	X	X	X	X	X	X
Survival Status		X	X	X	X	X	X	X	X	X	X	X	X	X
Patient Reported Outcomes														
Lee chronic GVHD Symptom Scale	X		X		X	X	X	X	X	X	X	X	X	X
QOL-SF-36v.2	X		X		X	X	X	X	X	X	X	X	X	X
AM-PAC Basic Mobility Outpatient Routine Short Form	X		X		X	X	X	X	X	X	X	X	X	X
Study Therapy														
ECP 			X											
Itacitinib 			X											
Immune suppression 			X											
Documentation of systemic corticosteroid dose		X	X	X	X	X	X	X	X	X	X	X	X	X

Short Title: FLIGHT

Version Date: 28JAN2022

Protocol Activities	Screening 	On-Treatment Period: One Cycle = 28 days									Off Treatment Period		
		Lead-In 	Cycle 1		Cycle 2 & 3	Cycle 4	Cycle 5	Cycle 6	Cycle 7	Cycles 8 – 12	PD Visit 	EOT 	Follow-Up 
Week			1	3	5 & 9	13	17	21	25	29 – 45			
Day of the Cycle (Visit Window)	(-28 days)	-10 to -5 days	1 	15 (+ 3 days)	1 (± 5 days)	1 (± 7 days)	1 (± 7 days)	1 (± 7 days)	1 (± 7 days)	1 (± 7 days)		30 days from last dose	Every 12 weeks
Correlative Studies													
Blood for correlative studies 	X		X 						X		X	X 	

 Screening procedures must be completed  $\leq$  28 days prior to the start of itacitinib lead-in.

 Itacitinib dosing will begin 5 to 10 days prior to C1D1.

 Progressive Disease visit should occur at the time that disease progression is found (+7 days). PFT's should be completed within 4 weeks of the PD visit.

 End of Treatment visit should occur 30 days ( $\pm$  7 days) after the last treatment dose of itacitinib.

 Patients will be followed for survival and disease status after coming off treatment. These visits should occur every 3 months for up to 12 months after coming off-treatment.

 All procedures must be completed prior to the start of study therapy.

 Demographic information will include the following: change in residence, annual income, insurance type, and employment status.

 See Appendix 1: Karnofsky Performance Status.

 Pulmonary function tests (PFT) with spirometry are required at screening. Only Spirometry is required at C4D1, C7D1, C10D1, and at the EOT or PD visit. PFTs and/or spirometry may be conducted  $\leq$  7 days prior to the scheduled day one visit to allow for timely review of results.

 Patients will be instructed to walk without assistance for 2 minutes and the distance traveled in feet will be recorded in the eCRF. This will occur at C1D1, C2D1, C3D1, C6D1, C8D1, C10D1, and EOT or PD visit.

 Adverse events will be collected for the duration of study therapy and end 30 days after the last dose of study drug. The relationship of the event to itacitinib, ECP, GVHD, and other causes (transplant, conditioning regimen, or other immunosuppressants) will be assessed as definite, probable, possible, unlikely, or not related.

 Hematology includes CBC with differential and platelets.

 Chemistry includes a LDH, magnesium, phosphorus, and a CMP (Albumin, Alkaline Phosphatase, Aspartate Aminotransferase, Alanine Aminotransferase, Total Bilirubin, Calcium, Carbon Dioxide, Creatinine, Chloride, Glucose, Total Potassium, Protein, Sodium, and Urea Nitrogen).

 Coagulation labs include PT/INR and PTT, to be collected at screening and as clinically indicated while on study.

 Lipid panel should include total cholesterol, triglycerides, HDL cholesterol, LDL cholesterol, and VLDL cholesterol. This will occur at C4D1, C7D1, C10D1, and EOT or PD visit.

 Women of child-bearing potential will require a negative pregnancy test within  $\leq$  7 days of initiating itacitinib therapy.

 HIV and hepatitis testing should include HIV, hepatitis B surface antigen, hepatitis B surface antibody, hepatitis B core antibody, HCV antibody, HBV-DNA, and HBC-RNA. HBV-DNA and HBC-RNA are only required if antigen and antibody testing is positive. Prior HIV screening results obtained as standard of care for allo-HCT confirming an HIV-negative status may be used for determining eligibility, and tests do not need to be repeated. Prior test results obtained as part of standard of care before allo-HCT confirming that a participant is immune and not at risk for reactivation (ie, hepatitis B surface antigen negative, surface antibody positive) may be used for purposes of eligibility, and tests do not need to be repeated.

 Quantitative immunoglobulins to include IgA, IgG, and IgM will be drawn C1D1, C4D1, C7D1, C10D1, EOT or PD visit.

 Absolute CD4 Count will be drawn C1D1, C4D1, C7D1, C10D1, EOT or PD visit

 Monitoring for infection will be performed at screening and for the duration of study therapy per institutional practice. Testing for cytomegalovirus and Epstein-Barr virus will be performed at screening. Prior test results obtained as part of standard of care before allo-HCT may be used for purposes of eligibility and tests do not need to be repeated. Routine infection monitoring should occur during the study as per institutional practice and include at a minimum PCR

testing on plasma for CMV and EBV and monitoring for fungal infections (i.e. Aspergillus). Additional monitoring should be performed during treatment if there is clinical suspicion of an infection.

 Screening assessment may be used if completed within 7 days prior to C1D1.

 Graft failure/chimerism should be performed on whole blood and should include: Chimerism, Post-Transplant and Chimerism, Post-Cell Sort, T cells.

 Participants will be closely monitored for any evidence of underlying disease relapse or recurrence during study therapy. These evaluations will be conducted in accordance with local institutional practices.

 To be completed prior to the physical exam at C1D1, C2D1, C3D1, C6D1, C8D1, C10D1, and EOT or PD visit.

 ECP will be given at a frequency of twice weekly for 8 weeks followed by a standard taper schedule as per study protocol. Refer to Table 4 for taper schedule.

 All patients will undergo 5 to 10 days of itacitinib monotherapy. The first ECP treatment will be considered C1D1. On days that the patient is being seen in clinic, itacitinib dosing does not need to be held prior to routine blood draws or for correlative studies.

 Patients may be on immune suppression at the time of study enrollment. On days that the patient is being seen in clinic, immunosuppressives should be held until after the blood draws if trying to achieve a therapeutic level. See Section 6.1.3.

 Correlative studies are only required during dose expansion. On days of drug administration, correlative blood samples should be drawn without regard to itacitinib dosing or ECP therapy. Patients should take itacitinib at their usual time. Blood will be drawn at screening, C1D1, the time of response, C7D1, and at EOT or progression, whichever occurs first.

 Only to be drawn from the first nine patients enrolled in Part 2, Dose Expansion.

 To be collected from participants who complete 12 cycles of therapy.

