## 1 OBJECTIVES

### 1.1 Primary Objective

**1.1.1 Part 1:** To assess an appropriate dose of itacitinib in combination with Extracorporeal Photopheresis (ECP) in patients with moderate or severe chronic GVHD.

Primary Endpoint: The rate of dose-limiting toxicities during the defined DLT evaluation period.

**1.1.2 Part 2:** To assess the clinical efficacy of itacitinib in combination with ECP in subjects with moderate or severe chronic GVHD treated at the Recommended Phase 2 Dose (RP2D).

Primary Endpoint: Overall response rate (ORR) at 24 weeks (at Cycle 7 Day 1 visit) as determined by the NIH Consensus Development Project Criteria (ORR is defined as CR + PR) without secondary systemic immunosuppressive therapy and no recurrent malignancy or death.

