### 1.3 Exploratory Objective(s)

#### 1.3.1 To assess patient-reported outcomes.

Exploratory Endpoint: The change in symptom scores using the QOL-SF-36-v2 questionnaire, Lee Chronic GVHD Symptom Scale, and the Activity Measure for Post Acute Care (AM-PAC) Basic Mobility Outpatient Routine Short Form at 24 weeks and 1-year.

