#### **Patient-Reported Outcomes**

As assessed by the change in QOL-SF-36-v2 questionnaire, Lee Chronic GVHD Symptom Scale, and Activity Measure for Post Acute Care (AM-PAC) Basic Mobility Outpatient Routine Short Form scores at 24 weeks.

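### Footnote 24 and the Table 7 grid disagree on the patient-reported outcome visits, including Cycle 7 Day 1, the 24-week visit

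*Combined protocol and SAP*

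**What the plan says.** - **Endpoint.** Section 1.3.1 sets the change in SF-36, Lee scale and AM-PAC scores as an exploratory endpoint, ending with "Basic Mobility Outpatient Routine Short Form at 24 weeks and 1-year". Section 12.4.3 (Patient-Reported Outcomes) names one time only: "Basic Mobility Outpatient Routine Short Form scores at 24 weeks".
- **Which visit is week 24.** Section 1.1.2 fixes it for the primary endpoint: "Overall response rate (ORR) at 24 weeks (at Cycle 7 Day 1 visit".
- **The grid.** In Table 7 (Section 8) the three instrument rows are identical. As extracted, the SF-36 row reads "QOL-SF-36v.2 X X X X X X X X X X X X". After blanks at the lead-in and at Cycle 1 Day 15, the marks run without a gap from Cycles 2 and 3 onward.
- **The footnote.** Footnote 24, attached to the heading of the patient-reported block, says "To be completed prior to the physical exam at C1D1, C2D1, C3D1, C6D1, C8D1, C10D1, and EOT or PD visit".
- **Elsewhere.** Section 10.11 refers the AM-PAC back to the Schedule of Events. Section 10 has no entry for the Lee scale or the SF-36. No rule says whether a footnote or a grid mark takes precedence.

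**The concern.** The one time point that the statistical section names for these questionnaires is the visit that the footnote leaves out. A coordinator has two instructions in the same table and no means of choosing between them.

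Reading the footnote as the working visit list is natural here. Footnotes 9, 15, 18 and 19 each narrow the broad mark for Cycles 8 to 12 down to C10D1. Those four footnotes also name C7D1, so its absence from footnote 24 stands out.

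At stake is the 24-week change score in patients whose site follows the footnote. A questionnaire not given at the visit cannot be recovered later, and a value from a neighbouring visit would not line up with the primary response assessment.

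**Working it through.** **Inputs.** Cycle length: "On-Treatment Period: One Cycle = 28 days" (Table 7 header). Visit window from Cycle 4 on: ±7 days (Table 7). End of treatment (EOT): "End of Treatment visit should occur 30 days" (±7 days) after the last itacitinib dose (footnote 4). Week-24 visit: C7D1 (Section 1.1.2). Days are counted from C1D1.

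**Step 1. Reproduce the plan's week labels.** Day of Cycle k Day 1 = 28(k − 1) + 1; week label = 4(k − 1) + 1; completed weeks = 4(k − 1). For k = 7: day 28 × 6 + 1 = 169, week 25, 24 completed weeks. Table 7 labels Cycle 7 as week 25. The same formula gives its other Day 1 labels (1, 5 and 9, 13, 17, 21, 29 to 45), so C7D1 is the 24-week visit in the schedule as well as in Section 1.1.2.

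**Step 2. Compare the two visit lists.**

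| Visit | Grid, all three instruments | Footnote 24 |
|---|---|---|
| Screening | marked | not listed |
| C1D1 | marked | listed |
| C2D1, C3D1 | marked | listed |
| C4D1, C5D1 | marked | not listed |
| C6D1 | marked | listed |
| **C7D1** | **marked** | **not listed** |
| Cycles 8 to 12 (one column) | marked | C8D1 and C10D1 only |
| Progression, EOT | marked | listed |
| Follow-up | marked | not listed |

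The extracted instrument rows have 14 cells against 13 header columns, so the alignment needs a check. Cycle 7 is the ninth column, and cells 5 to 14 are all marked. A shift of one column either way still leaves Cycle 7 marked.

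**Step 3. See whether a listed visit can stand in for C7D1.**

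| Visit | Day | Window | Completed weeks |
|---|---|---|---|
| C6D1 | 28 × 5 + 1 = 141 | 134 to 148 | 20 |
| C7D1 | 28 × 6 + 1 = 169 | 162 to 176 | 24 |
| C8D1 | 28 × 7 + 1 = 197 | 190 to 204 | 28 |

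The windows are 162 − 148 = 14 days apart on one side and 190 − 176 = 14 days apart on the other. If itacitinib stops at the end of Cycle 6 (assumed last dose on day 28 × 6 = 168), EOT falls on day 168 + 30 = 198 (191 to 205), also outside. Of the visits in the footnote, only a progression visit could fall in the C7D1 window, and only by chance.

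**Step 4. Recall periods.** The Lee scale asks about the past month (Appendix 8), and SF-36 items 13 to 32 ask about the past four weeks (Appendix 9). Taking a month as 28 days, C7D1 covers days 141 to 168, C6D1 covers days 113 to 140, and C8D1 covers days 169 to 196. At nominal visit days, neither neighbour covers the four weeks before the primary assessment.

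**Step 5. Later substitutes differ by outcome.** Patients with PR or better may stay on itacitinib beyond week 24 (Section 4.1), so their C8D1 value is taken on drug. A patient who stops at week 24 gives an EOT value about 30 days off drug, near the same calendar day.

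**Step 6. The 1-year point.** For a patient completing 12 cycles, the last dose is on day 28 × 12 = 336 and EOT on day 366, or 366 / 7 = 52.3 weeks. EOT is in the footnote, so for such patients the omission bears on week 24 and not on 1 year.

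**Step 7. Scope.** The secondary patient-reported severity endpoint (Section 1.2.2) uses the Appendix 6 form. Section 10.9 collects that form with the chronic GVHD assessment, whose own Table 7 row is marked at Cycle 7 and is not under footnote 24.

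**The case against.** The strongest reply is that the grid already requires the questionnaires at Cycle 7. A reader who sees only the footnote might infer that the 24-week values will not be collected at all. The documents do not support that: all three rows mark Cycle 7, and no rule gives the footnote precedence. Read as exhaustive, the footnote would also cancel the marks at screening, Cycles 4 and 5, and follow-up. It could instead be read as a timing rule only, asking for completion before the physical exam. This reply stands against any claim of certain loss. It does not remove the contradiction, because the footnote does name visits, and even as a timing rule it leaves C7D1 without one.

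A second reply is that little depends on these data. That is largely right. The endpoint is exploratory, Section 12.4.3 attaches no test to it, and no decision rule uses it. A reader might also infer that every patient-reported result at 24 weeks is at risk; the Appendix 6 form shows otherwise.

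A reader might further infer a copying slip. The 2-minute walk footnote (footnote 10) has the same list, "This will occur at C1D1, C2D1, C3D1, C6D1, C8D1, C10D1, and EOT or PD visit", and the walk-test row, unlike the questionnaire rows, is blank at Cycle 7. That origin is plausible, but the documents do not state it, and the point does not need it.

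**Conclusion.** The point holds as an internal contradiction in Table 7 that puts the 24-week exploratory questionnaire data at risk. It does not establish that the data will be missing.

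The size depends on site behaviour, which the documents do not give. If every site follows the grid, no C7D1 questionnaire is lost for this reason; if every site follows the footnote, all are. This range is not an estimate. Where the visit is skipped, the nearest scheduled values are 28 days away on either side, in non-overlapping windows. Sample size, error rates, the primary endpoint and the secondary patient-reported severity endpoint are unaffected.

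The conclusion assumes that 24 weeks means C7D1 for the questionnaires, as Section 1.1.2 states for the primary endpoint, and that the marks in the extracted grid reflect the printed table to within one column. The correction is more than clerical, because following the footnote as written would lose the one measurement that Section 12.4.3 plans to analyse.

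**What to change.** Add C7D1 to footnote 24. Then reconcile the footnote with the grid at screening, Cycles 4 and 5, and follow-up, and state which of Cycles 8 to 12 are meant, so that both list the same visits. If the footnote is meant only as a timing rule, reword it to say that the questionnaires precede the physical exam at every visit marked in the grid.

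With C7D1 listed, the questionnaires fall on day 169 (window 162 to 176), after 24 completed weeks, which agrees with Sections 1.1.2, 1.3.1 and 12.4.3.

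The cost is a few words in a footnote, plus a decision on the other mismatched visits. Section 16.8 requires IRB review of any change, so it can go with the next amendment. Meanwhile sites can be reminded that the approved grid already marks Cycle 7. The burden on patients is three short questionnaires at a visit that already takes place. If enrolment has begun, the report should give the number of patients with a questionnaire inside the C7D1 window.
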